4.1.2.4. Clinical Studies

PT2385 has not previously been studied in patients with VHL disease. Clinical studies of PT2385 in ccRCC are ongoing. Under Protocol PT2385-101, patients with advanced ccRCC who had been treated with at least 1 prior treatment with a VEGF inhibitor were treated with PT2385 twice daily in a 3+3 Phase 1 design to determine the maximum tolerated dose (MTD)/RP2D and to evaluate safety, PK, and pharmacodynamics (PD). The 26 patients enrolled in the dose-escalation portion received PT2385 at oral dosages of 100 to 1800 mg twice daily. No dose limiting toxicities (DLTs) were observed at any dose level. Exposure generally increased with dose up to the 800 mg dose, without a further increase from 800 to 1800 mg. At 800 mg, PT2385 was rapidly absorbed with a C_{max} of 3.14 µg/mL and a $t_{1/2}$ of 17 hours. The targeted C_{min} of 280 ng/mL was exceeded in the majority of patients receiving a twice daily dose of \geq 800 mg. Circulating plasma levels of EPO rapidly decreased within 24 hours in most patients receiving \geq 800 mg and remained suppressed during the 16-week sampling period. Based on safety, PK, and EPO PD data, the RP2D has been defined as oral 800 mg twice daily. An additional 25 patients were enrolled in an expansion cohort at the RP2D. As of August 15, 2016, the most common adverse events (AEs) of any severity have been anemia, peripheral edema, and fatigue. One patient had a complete response (CR), 4 patients had a partial response (PR), and 16 patients had stable disease (SD) for more than 16 weeks. PT2385 administration was safe and well tolerated, and has demonstrated early evidence of clinical activity in these heavily pre-treated patients with advanced ccRCC (Courtney et al, 2016).

A Phase 1 food effect study of PT2385 was conducted in healthy female volunteers. The most common AEs were headache, injection site bruising, and nausea. The presence of food had a mild effect (19% to 37% increase) on the exposure to PT2385 in this study; little to no effect was observed in exposure to PT2639, the major metabolite, in the presence of food.

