8.2. Concomitant Medications

Patients may not receive chemotherapy, anti-neoplastic hormonal therapy, or any investigational anti-neoplastic agent during the course of this study. Immunosuppressive agents are prohibited during the course of study participation. Systemic steroids may not be used in the study at doses greater than the equivalent of 20 mg prednisone daily with the exception of intermittent use for the treatment of emesis.

Patients may receive limited fraction palliative radiotherapy after 12 weeks to control local tumor-related symptoms if irradiation is unlikely to induce major organ toxicity and only if in the opinion of the Investigator, the patient does not have progressive disease. The radiation field cannot encompass a target lesion. Radiation to a target lesion is considered progressive disease and the patient should be removed from study treatment.

Antiemetic agents may be used for the treatment of nausea and vomiting but may not be administered prophylactically. Granulocyte colony-stimulating factor (G-CSF) should be administered only for severe or prolonged neutropenia or for neutropenic sepsis. There will be no constraint on the use of growth factors during subsequent treatment; however, prophylactic use is discouraged and adherence to the American Society of Clinical Oncology (ASCO) guidelines is recommended. Erythropoietin should not be administered during the first 28 days of study drug treatment.

Patients should receive all necessary supportive care, including blood products, transfusions, antibiotics, pain medications, bisphosphonates, and replacement hormonal therapies (insulin, thyroid hormones, estrogen/progesterone) as needed, but levels should be closely monitored.

PT2385 is primarily metabolized by UGT2B17, UGT2B7, UGT2B15, CYP2C19 and CYP3A4. Strong inhibitors of CYP2C19 and CYP3A4 should be avoided in patients receiving PT2385 (Appendix 6).

PT2385 has been shown to induce the enzymes CYP3A4 and CYP2B6 in cultured human hepatocytes. Simcyp PBPK model simulations indicate weak-to-moderate CYP3A4 substrate midazolam DDIs (~50% reduction in midazolam AUC) at the clinically relevant PT2385 doses. Simulations also indicate that PT2385 is a weak CYP2B6 inducer (< 11%

Peloton Therapeutics, Inc. CONFIDENTIAL

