10.1.2. Pharmacodynamics and Biomarker Assessments

Blood samples for analysis of PD effects (biomarkers) will be obtained at the Week 1, Day 1 visit before and 6 hours after study drug administration. Pharmacodynamic biomarkers to be assessed may include, but are not limited to, levels of EPO and VEGFA. Whole blood samples will be collected for single nucleotide polymorphism analyses of genes (231) encoding proteins that may be involved in the transport or metabolism of PT2385.

Details for the collection, processing, storage, and shipment of samples for the determination of PD effects can be found in the study laboratory manual.

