13.3.5. Pharmacodynamic Analyses

Blood samples for assessment of pharmacodynamic parameters such as EPO will be obtained in conjunction with PK samples, before (pre-dose) and 6 hours after study drug administration at the Week 1 visit and only before study drug administration at the Week 3 and 5 visits.

The value, change from baseline, and percent change from baseline will be listed and summarized for each scheduled time-point during the study for each of the pharmacodynamic parameters.

To investigate the effect of these potential biomarkers on efficacy, the association of baseline pharmacodynamic parameters with ORR and PFS will be investigated using exploratory multivariate techniques, subgroup analyses, and regression modeling.

The summaries will be based on the Safety Analysis Set. The exploratory analyses will be performed for the Efficacy Analysis Set.

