20. APPENDICES

- Appendix 1 Schedule of Events
- Appendix 2 ECOG Performance Status
- Appendix 3 RECIST 1.1 Summary
- Appendix 4 Evaluation of Non-Renal VHL Related Disease
- Appendix 5 New York Heart Association Functional Classification
- Appendix 6 Partial List of Strong CYP2C19 and CYP3A4 Inhibitors
- Appendix 7 Partial List of Substrates of CYP3A4, CYP2B6, CYP2C9, and CYP2C19

Appendix 1	Schedule of Events
------------	--------------------

	Treatment Period				Post-Treatment Period/ Early Termination		
Assessment	Screening (Day -28 to Day -1)	Week 1 ¹ (Day 1)	Weeks 3 and 5 ¹ (± 1 Day)	Weeks 9, 13, 17, and Every 4 Weeks ¹ (± 2 Days)	Extended Treatment ² Every 12 Weeks (± 1 Week)	Safety Follow-Up 28 Days After Last Dose of Study Drug Taken (± 7 Days)	Long Term Follow-up (every 6 months) ¹⁶
Informed Consent	Х						
Assess Inclusion/Exclusion	Х						
Demographics and Medical	Х						
Physical Examination ³	Х	Х	Х	Х	Х	Х	
Vital Signs ⁴	Х	X 4	X	Х	Х	Х	
Weight	Х	Х	Х	Х	Х	Х	
Height	Х						
ECOG	Х	Х	Х	Х	Х	Х	
Dispense/Collect Study Drug		Х	Х	Х	Х		
Hematology ⁵	Х	Х	Х	Х	Х	Х	
Serum Chemistry ⁶	Х	Х	Х	Х	Х	Х	
PT, aPTT, INR	Х						
Iron Panel ⁷	Х	Х	Х	Х		Х	
Urinalysis ⁸	Х	Х	Х	Х	Х	Х	
Pregnancy Test ⁹	Х	Х	Х	Х	Х	Х	
ECG ¹⁰	Х	X^{10}	X^{10}	X^{10}			
Tumor Assessment ¹¹	Х			X ¹¹	Х		
Pharmacokinetic Sample ¹²		Х	Х	Х			
Pharmacodynamic Sample ¹³		Х	Х	Х			
Assessment of Male Fertility ¹⁴	Х			X ¹⁴		X ¹⁴	
Tissue Sample Collection ¹⁵	Х						
Adverse Events		Х	Х	Х	Х	Х	
Concomitant Medications	Х	X	X	X	Х		
Study Drug Administration				X			
Patient Status ¹⁶							X

ECG = electrocardiogram; ECOG = Eastern Cooperative Oncology Group; PT/aPTT = prothrombin time/activated partial thromboplastin time.

Peloton Therapeutics, Inc. 08LQCONFIDENTIAL

- 1. Assessments are to be done on Day 1 of each visit week. For the Weeks 3 and 5 visits, assessments may be ± 1 day; for the Week 9, 13, and 17 visits and for visits every 4 weeks thereafter, assessments may be ± 2 days.
- 2. For patients deriving clinical benefit at 1 year and continuing to take study drug after 1 year, visits will be conducted at 12-week intervals.
- 3. Funduscopic exams must be performed at Screening, Baseline, and every 12 weeks during the treatment period.

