- 11. Tumor assessment including non-contrast or contrast computed tomography (CT), or magnetic resonance imaging (MRI) will be obtained at screening and within 7 days before the Week 13 visit, and every 12 weeks thereafter (e.g., before the visits for Weeks 25, 37, etc.).
- 12. At the Week 1 visit, patients will take their morning dose of PT2385 in the clinic and will have 4 mL of blood drawn for pharmacokinetic (PK) assessment before (pre-dose) and 6 hours after study drug administration. At the Week 3, 5, 9, 13, and 17 week visits, patients will take their morning dose of PT2385 in the clinic. The blood sample for PK assessment is to be obtained before study drug administration on these days.
- 13. Blood samples for analysis of pharmacodynamic effects of PT2385 (e.g., erythropoietin) will be obtained in conjunction with PK samples, before (pre-dose) and 6 hours after study drug administration at the Week 1 visit and only before study drug administration at the Weeks 3, 5, 9, 13 and 17 visits; patients should not take their dose of PT2385 until after this blood collection has occurred at these visits. Two whole blood samples will be collected at the Week 1 visit only for sequencing of genes encoding proteins that may be involved in regulating PT2385 metabolism.
- 14. Tests (orchidometry, semen analysis, and measurement of testosterone, follicle stimulating hormone, luteinizing hormone, and inhibin B levels) are to be conducted at Screening, the Week 17 visit, and 13 weeks after last study drug administration for those male patients for whom a clinically significant effect on fertility was seen at Week 17.
- 15. Archival tumor tissue samples will be obtained whenever possible from all patients. Additionally, fresh tissue sample will be obtained from consenting patients in whom tumor tissue is accessible (patients who undergo tumor excision during the study).
- 16. Long-term follow-up may be accomplished via an in person visit or telephone. The patient will be questioned about the following since their last study visit or telephone contact: medical history, surgical history, disease status, and survival status.

Peloton Therapeutics, Inc. 08LQCONFIDENTIAL

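### Serum EPO values taken after exogenous erythropoietin have no analysis rule, and if Appendix 1 governs, three scheduled visits fall after the 28-day bar ends

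*Combined protocol and SAP*

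**What the plan says.** Section 8.2 sets the only limit on erythropoietin: "Erythropoietin should not be administered during the first 28 days of study drug treatment". The same paragraph says of growth factors generally: "There will be no constraint on the use of growth factors during subsequent treatment". It then discourages prophylactic use and recommends following the ASCO guidelines.

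The pharmacodynamic sampling schedule is stated in three ways:

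- Section 10.1.2: samples "will be obtained at the Week 1, Day 1 visit before and 6 hours after study drug administration". No later visit is named.
- Section 13.3.5: the two Week 1 samples, then "only before study drug administration at the Week 3 and 5 visits".
- Appendix 1, footnote 13: the two Week 1 samples, then "only before study drug administration at the Weeks 3, 5, 9, 13 and 17 visits". The grid agrees, marking this sample in the column that holds Weeks 9, 13 and 17.

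On analysis, section 13.3.5 says the value, change and "percent change from baseline will be listed and summarized for each scheduled time-point during the study". It also plans to relate baseline pharmacodynamic values to ORR and PFS. Neither 13.3.5 nor the missing-data rules in 13.3.1 say what happens to an EPO value drawn after erythropoietin was given. Section 8.2 has all concomitant medication recorded during the study and for the 28 days before first dose.

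**The concern.** Serum EPO is the one marker named in the exploratory objective (5.3). Erythropoietin given as a drug may add to the serum level that the trial measures, in the direction opposite to the fall expected from PT2385. Its use is foreseeable: section 4.1.2.4 reports that in the first study in humans "the most common adverse events (AEs) of any severity have been anemia, peripheral edema, and fatigue", and 8.2 itself anticipates it.

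The late samples matter most for comparison. Section 4.1.2.4 describes EPO suppression over a 16-week sampling period in that study, and Week 17 Day 1 of this trial is 16 weeks after first dose. These are also the samples that the bar does not protect.

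Use may be selective. Patients whose EPO falls furthest may be the ones who become anemic and are treated, so a strong drug effect could appear in the summary as a rise.

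A secondary route runs through baseline. Eligibility qualifies hemoglobin by recent transfusion only; no criterion addresses erythropoietin before Day 1. A patient who had been receiving it could have a raised baseline and then show a fall not due to PT2385. That baseline value also enters the association with ORR and PFS.

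**Working it through.** The plan states no figure on this point, so there is none to reproduce. The check has two parts.

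**1. Which samples fall after the bar.** Appendix 1 states: "Assessments are to be done on Day 1 of each visit week". So Week w falls on Day 7(w - 1) + 1. Its windows are ±1 day for Weeks 3 and 5, and ±2 days for Weeks 9, 13 and 17.

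| Visit | Day | Window | Against Days 1-28 |
|---|---|---|---|
| Week 1 | 1 | 1 | inside |
| Week 3 | 15 | 14-16 | inside |
| Week 5 | 29 | 28-30 | at the edge |
| Week 9 | 57 | 55-59 | after |
| Week 13 | 85 | 83-87 | after |
| Week 17 | 113 | 111-115 | after |

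- Under Appendix 1: 2 + 5 = 7 samples. Three are clearly after the bar, and Week 5 may be if drawn on Day 29 or 30.
- Under 13.3.5: 2 + 2 = 4 samples. At most one, Week 5, can be affected.
- Under 10.1.2: 2 samples, none affected.

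Week 17 is (113 - 1)/7 = 16 weeks after first dose.

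**2. How far a visit summary could move.** Let f be the share of patients treated, e the true change under PT2385, and k the measured EPO in treated patients as a multiple of baseline. All three are assumptions; the documents give none of them.

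Mean change = (1 - f)e + f(k - 1). With e = -50%:

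- f = 6%, k = 2: 0.94 × (-50) + 0.06 × 100 = -41%. With k = 5: -47 + 24 = -23%. With k = 20: -47 + 114 = +67%.
- f = 10%, k = 2: 0.90 × (-50) + 0.10 × 100 = -35%. With k = 5: -45 + 40 = -5%.
- f = 20%, k = 2: 0.80 × (-50) + 0.20 × 100 = -20%. With k = 5: -40 + 80 = +40%.

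The mean reaches zero at f = -e/(k - 1 - e). For e = -50%, this is 0.5/1.5 = 33% at k = 2, 0.5/4.5 = 11% at k = 5, and 0.5/19.5 = 2.6% at k = 20. Over e from -30% to -70% and k from 2 to 20, the zero point runs from 0.3/19.3 = 1.6% to 0.7/1.7 = 41%.

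Section 13.3 reports the median as well as the mean. If all treated values lie above the rest, the reported median is the 0.5/(1 - f) quantile of the untreated patients: 0.5/0.9 = 0.556 at f = 10%, about the 56th percentile. The median is therefore much more stable.

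**The case against.** The strongest reply is that the problem may barely exist. Section 13.3.5, the analysis section itself, stops sampling at Week 5, where the 28-day bar covers nearly everything, and 10.1.2 stops at Day 1. Sampling to Week 17 rests on Appendix 1. This stands: the later-visit problem is conditional on Appendix 1. It does not dispose of the point. The Appendix 1 grid and footnote agree with each other, and 13.3.5 ties these draws to the PK samples, which sections 11 and 13.3.7 continue to Week 17.

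Second, use may be rare. Section 8.2 discourages prophylactic use and recommends guideline adherence. The anemia report comes from heavily pre-treated patients with advanced disease, whereas this trial requires hemoglobin of at least 9 g/dL and excludes metastatic disease and prior systemic therapy for ccRCC. This stands, and the frequency is unknown.

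Third, section 13 defers detail to a formal SAP, and recorded medication lets affected values be found later. True, but a rule written before the data are summarised is better than one chosen afterwards.

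Fourth, exclusion is itself selective: if treated patients had the deepest suppression, dropping their later values understates the effect. This stands and shapes the fix.

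**Conclusion.** The gap is real but narrow. If the Appendix 1 schedule governs, EPO values at Weeks 9, 13 and 17, and possibly Week 5, are confounded in any patient given erythropoietin by then, and the plan as written would pool them with the rest. The size cannot be stated, because no rate of use is given. The illustration shows only that a mean can be sensitive to a few treated patients while the median is not.

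A reader might infer more than the documents support:

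- That treated patients' values measure the administered product instead of PT2385. The documents give no dose timing relative to sampling and do not say what the assay detects. Confounding by both sources is as far as they go.
- That efficacy conclusions are at risk. The primary ORR analysis is untouched, and erythropoietin given on study cannot alter a baseline value, so it cannot bias the baseline association with ORR and PFS. Only use before Day 1 could, and that is a secondary matter of unknown frequency.

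What is affected is an exploratory, descriptive summary. The repair is cheap enough to be worth making.

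**What to change.** All changes concern the analysis and the consistency of the text. No change to the clinical rule on erythropoietin is proposed.

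1. Reconcile the pharmacodynamic sampling schedules in 10.1.2 (Week 1), 13.3.5 (Weeks 1, 3 and 5) and Appendix 1 (Weeks 1, 3, 5, 9, 13 and 17).
2. Add to 13.3.5, or to the formal SAP: *Serum EPO values taken after a patient's first on-study dose of an erythropoiesis-stimulating agent are flagged in the listing and left out of the main EPO summary. The number left out is shown at each visit. A summary of all values is given as a sensitivity analysis.* The second summary is needed because the exclusion is itself selective.
3. Add: *Patients with such an agent recorded in the 28 days before Day 1 are flagged, and the change-from-baseline EPO summaries and the baseline-EPO association analyses are repeated without them.*

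Cost: a short rule and one extra table. The medication data are already collected under 8.2, so no new data are needed. The downside is fewer EPO values in the main summary at later visits.

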8.3. Treatment Compliance

The Investigator or his/her designated and qualified representatives will dispense study drug only to patients enrolled in the study in accordance with the protocol. The study drug must not be used for reasons other than that described in the protocol.

The number of tablets returned at a visit will be used to assess compliance; any discrepancy from the expected number of returned tablets will be discussed with the patient.

Patients who fail to comply with the requirements of the study may be withdrawn from the study.

8.4. Randomization and Blinding

There will be no randomization or blinding in this open-label study.

9. STUDY DRUG MATERIALS AND MANAGEMENT

9.1. Study Drug

PT2385 tablets are supplied by Peloton Therapeutics, Inc. as immediate-release 200 mg tablets for oral administration. Each PT2385 tablet contains PT2385, lactose monohydrate, microcrystalline cellulose, croscarmellose sodium, hydroxypropyl cellulose, polysorbate 80, and magnesium stearate.

9.2. Study Drug Packaging and Labeling

The 200 mg strength of PT2385 will be supplied in 100-cc high-density polyethylene bottles with induction-seal liners and a child-resistant closure. Each bottle of study drug will contain 60 tablets of a single strength (200 mg) of PT2385.

Bottles provided to the site will be labeled with the following information:

- 1. PT2385, 200 mg
- 2. Protocol PT2385-202
- 3. Lot number
- 4. Contains 60 200 mg PT2385 tablets
- 5. Instructions: Take orally as directed
- 6. CAUTION: New Drug limited by federal law to investigational use
- 7. FOR ORAL USE ONLY
- 8. Store at controlled room temperature 15°C to 30°C (59°F to 86°F)
- 9. Peloton Therapeutics, Inc., Dallas, TX

9.3. Study Drug Storage

PT2385 must be stored in a secure location at controlled room temperature, 15°C to 30°C (59°F to 86°F).

9.4. Study Drug Preparation

PT2385 will be provided to each site pharmacy and the Investigator or designee will provide tablets to each patient with clear instructions on the number of tablets to be taken each day until the next study visit.

9.5. Administration

Following confirmation of eligibility, enrolled patients will be assigned to open-label PT2385. Four PT2385 200 mg tablets will be taken orally twice daily (for a total of 8 tablets or 1600 mg daily), with doses approximately 12 hours apart. Study drug may be administered without regard to food.

Missed doses may be made up if taken within 4 hours after the scheduled administration time. Study drug may not be taken within 8 hours before the scheduled time for administration of the next dose. Patients who vomit after study drug administration should not retake that study drug dose but should resume taking study drug with the next scheduled dose.

9.6. Study Drug Accountability

The dispensing pharmacist or designated qualified individual will write the date dispensed and the patient's identification number or initials on the Drug Accountability Source Documents. All medication supplied will be accounted for on the Drug Accountability Record.

9.7. Study Drug Handling and Disposal

All partially used or unused study drug supplies will be destroyed at the site in accordance with approved written site procedures, or returned to Peloton Therapeutics or its designee as described in the pharmacy manual. The Investigator will maintain a record of the amount and dates when unused supplies were either destroyed or returned to Peloton Therapeutics or a designated vendor for destruction. All records will be retained as noted in Section 17.2.

10. ASSESSMENT OF EFFICACY

10.1. Efficacy Parameters

Primary endpoint: Best confirmed response in VHL disease-associated ccRCC tumors, defined as the proportion of the best confirmed response of CR or PR (as assessed by the Independent Review Committee (IRC)) as determined by RECIST 1.1, modified to follow ccRCC tumors only. ORR is defined as the proportion of patients with a best confirmed response of CR or PR.

Secondary endpoints:

- Progression-free survival (PFS) in VHL disease-associated ccRCC tumors, defined as the interval from the start of study treatment until the earlier of the first documentation of disease progression determined by RECIST 1.1 or death from any cause, and calculated for patients with a best confirmed response of CR or PR
- Duration of response (DOR) in VHL disease-associated ccRCC tumors, defined as the interval from the first documentation of response, as determined by RECIST 1.1, to the earlier of the first documentation of disease progression or death from any cause, and calculated for the patients with a best confirmed response of CR or PR
- Time to response (TTR) in VHL disease-associated ccRCC tumors, defined as the interval from the start of study treatment to the first documentation of a response, as determined by RECIST 1.1, and calculated for patients with a best confirmed response of CR or PR
- Best confirmed response, PFS, DOR, and TTR for non-ccRCC tumors associated with VHL disease in different organ systems, by modifying RECIST 1.1 criteria to assess tumors in individual organ systems (Appendix 4)

Exploratory endpoint:

• Changes in PD markers (e.g., serum EPO)

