5.2. Secondary Objectives

- To evaluate progression-free survival (PFS) in patients with VHL disease-associated ccRCC tumors treated with PT2385
- To evaluate duration of response (DOR) and time to response (TTR) in patients with VHL disease-associated ccRCC tumors treated with PT2385 who achieve a PR or better as determined by RECIST 1.1
- To study the effect of treatment with PT2385 on VHL disease-associated non-ccRCC tumors by modifying RECIST 1.1 criteria to assess tumors in individual organ systems independently rather than collectively
- To study the safety and tolerability of PT2385
- To study the pharmacokinetics (PK) of PT2385

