10.1.1. Response in VHL Disease-Associated ccRCC Tumors

Anti-tumor activity will be assessed by non contrast or contrast computerized tomography (CT) or magnetic resonance imaging (MRI) at baseline, within 7 days before the Week 13 visit and every 12 weeks thereafter. Patients will be imaged using the same technique at baseline and each follow up assessment.

Response assessments will be made using RECIST 1.1 (Appendix 3), modified to follow ccRCC tumors only. Best confirmed response and PFS will be determined for all patients. DOR and TTR will be determined for all patients with a best confirmed response of PR or CR. The ORR for VHL disease-associated ccRCC tumors will be determined.

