13. STATISTICS

This section describes the statistical methodology to be used in the analysis of protocol endpoints. These methods will be documented in a formal statistical analysis plan (SAP) detailing the analyses to be performed, which will be developed before the final database lock. The SAP will serve as the final arbiter of all statistical analyses. The SAP will describe the analysis of all safety, efficacy, PK, and PD response variables. Any changes to the methodology described in the final approved SAP will be presented and discussed in the clinical study report.

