13.3.4. Efficacy Analyses

The primary summaries of all response data will be based on the Efficacy Analysis Set.

Response of ccRCC tumors will be measured by contrast enhanced computerized tomography (CT) or magnetic resonance image (MRI) scan and assessed according to RECIST 1.1, modified to follow ccRCC tumors only.

Response assessments of ccRCC CR and PR should be confirmed by a second assessment. Where confirmed responses are required, the date of the first assessment will be used in all analyses. In the case that the confirmation assessment is not available, the assessment at the next scheduled time point will be used for confirmation. If there are no assessments, the response will be taken to be unconfirmed and a non response.

The ccRCC ORR is defined as the proportion of patients for whom the best confirmed ccRCC response is CR or PR, determined by RECIST 1.1. Estimates of the ccRCC ORR along with the associated 90% and 95% exact binomial confidence intervals (Clopper Pearson) will be provided. The binomial probability that the observed ccRCC ORR is > 0.15 will be calculated. Best confirmed ccRCC response will be summarized.

The ccRCC PFS is defined the interval from the start of study treatment until the earlier of the first documentation of ccRCC disease progression determined by RECIST 1.1 or death from any cause, whichever occurs first. Renal cell carcinoma PFS will be right censored for patients who meet one of the following conditions: 1) no post baseline disease assessments, 2) non protocol systemic anticancer treatment started before documentation of disease progression or death, 3) surgery that is considered to affect response before documentation of disease assessment visit, 5) alive and does not have documentation of disease progression before a data analysis cutoff date. The Kaplan-Meier (KM) method will be used to estimate the distribution of ccRCC PFS. Quartiles including the median will be estimated by KM method along with their 95% confidence intervals. A figure showing the estimated ccRCC PFS distribution will be provided. KM cumulative estimators along with the associated 95% CIs will be provided for ccRCC PFS rates at 26, 39 and 52 weeks. Duration of follow up for ccRCC PFS will be summarized according to the KM estimate of potential follow up also termed "reverse Kaplan-Meier."

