The ccRCC DOR will be calculated for patients who achieve a ccRCC CR or PR. For such patients, the ccRCC DOR is defined as the interval from first documentation of response, as determined by RECIST 1.1, to the earlier of the first documentation of disease progression or death from any cause. Dates of progression and censoring will be determined as described for the analysis of ccRCC PFS. Kaplan-Meier methods will be used to estimate the distribution of ccRCC DOR. Quartiles including the median will be estimated by KM method along with their 95% confidence intervals. KM cumulative estimators along with the associated 95% CIs will be provided for ccRCC DOR rates at 26, 39 and 52 weeks. These estimates will be used as estimates of durable response.

The ccRCC TTR will be calculated for patients who achieve a ccRCC CR or PR. Renal cell carcinoma TTR is defined as the interval from the start of study treatment to the first documentation of a ccRCC response of PR or better, as determined by RECIST 1.1.

The maximum percent decrease in ccRCC total tumor burden will be displayed using waterfall plots.

Summaries of the response endpoints will also be provided for subgroups of the Efficacy Analysis Set as follows: Subgroups will be defined according to blood level of PT2385 based on the PK assessments and duration of PT2385 treatment. The analyses of ccRCC ORR, ccRCC PFS, ccRCC best confirmed response, ccRCC DOR, and ccRCC TTR will be performed in each of these subgroups.

The ORR, PFS, best confirmed response, DOR, and TTR will be summarized for the nonccRCC tumors associated with VHL disease based on the subgroups of patients in the Efficacy Analysis Set who have the particular type of tumor. The determination of best response and date of progression will be determined by modifying RECIST 1.1 criteria to assess tumors in individual organ systems independently (e.g., VHL disease-associated solid tumors in the pancreas or adrenal gland, or hemangioblastomas or retinal angiomas).

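### Synopsis and Section 10.1 calculate ccRCC PFS only in confirmed responders, contradicting Sections 10.1.1 and 13.3.4; the endpoint definition is wrong as written

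*Combined protocol and SAP*

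**What the plan says.** The secondary endpoint list in Section 10.1 measures ccRCC PFS from the start of study treatment to the earlier of progression "or death from any cause, and calculated for patients with a best confirmed response of CR or PR". The synopsis list of secondary endpoints has the same wording.

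Other parts of the plan read differently:

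- Section 10.1.1: "Best confirmed response and PFS will be determined for all patients". Its next sentence limits only DOR and TTR to responders.
- Section 5.2: "To evaluate progression-free survival (PFS) in patients with VHL disease-associated ccRCC tumors treated with PT2385". The separate DOR/TTR objective does carry a responder condition.
- Section 13.3.4 bases the primary response summaries on the Efficacy Analysis Set, which Section 13.2 defines as everyone enrolled and dosed at least once. It defines PFS with no responder condition. Its first censoring category is "no post baseline disease assessments". It then says "The ccRCC DOR will be calculated for patients who achieve a ccRCC CR or PR" and restricts TTR in the same way.
- Synopsis, statistical methods: efficacy analyses use all patients with at least one dose. The responder condition is written for TTR, not for PFS.
- Section 13.3.5 relates baseline markers to ORR and PFS and adds: "The exploratory analyses will be performed for the Efficacy Analysis Set".

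On precedence, Section 13 says: "The SAP will serve as the final arbiter of all statistical analyses". The material supplied contains no separate SAP text.

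**The concern.** One endpoint has two populations. Both statements are complete, current text, and the protocol does not say whether Section 10.1 or Section 13.3.4 prevails.

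The responder-only version is not a usable PFS for treated patients. Time starts at first dose, but membership is decided later by a best confirmed CR or PR. Everyone who progresses without a confirmed response disappears, and those who remain carry a progression-free period that is guaranteed by how they were selected. The result would look favourable regardless of drug effect and would not answer the objective in Section 5.2.

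The faulty wording sits in the formal endpoint definition, which is where a SAP or report author would look first. The trial is open-label, so leaving the population to be settled later means settling it with outcomes visible.

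**Working it through.** The plan states no PFS sample size, event count or target, so there is no PFS figure to reproduce. The check is of the text, followed by the size of the consequence.

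**1. Which reading the text supports.** The strongest evidence is Section 10.1.1, which names all patients outright, and Section 13.3.4. A patient with no post-baseline assessment cannot be a confirmed responder, so the first censoring category would be empty under a responder-only endpoint. Section 13.3.4 also writes the restriction for DOR and TTR and omits it for PFS. The objective in Section 5.2 and the analysis set in Section 13.3.5 fit this reading but are weaker support.

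**2. Patients used.** Inputs from Section 13.1: N = 50, null ORR 0.15, alternative ORR 0.30, success at 13 or more responders.

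| Case | Patients in PFS | Left out |
|---|---|---|
| ORR 15% | 50 × 0.15 = 7.5 | 42.5 |
| Boundary 13/50 | 13 | 37 (37/50 = 74%) |
| ORR 30% | 50 × 0.30 = 15 | 35 |

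With the Efficacy Analysis Set, all 50 are included if all are dosed.

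**3. Guaranteed progression-free time.** The first scan is about week 12 and scans then follow every 12 weeks (Section 10.1.1; Appendix 1, footnote 11). A confirmed responder is therefore progression-free for at least about 12 weeks. Section 13.3.4 states no confirmation interval and gives the scheduled scan only as a fallback: "In the case that the confirmation assessment is not available, the assessment at the next scheduled time point will be used for confirmation". In that case the guarantee is 12 + 12 = about 24 weeks, and the next scan that can show progression is at week 36. No such patient can then have a scan-documented progression before the 26-week landmark.

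**4. Illustration of the bias.** None of these assumptions is in the documents: exponential progression with median m, progression recorded at 12-weekly scans, deaths ignored, first response at week f = 12, 24 or 36 with weights p = 0.5, 0.3, 0.2, and response unrelated to hazard. Confirmation comes c weeks later: c = 12 (next scheduled scan) or c = 4 (an extra scan that is not in the schedule). Let s be the last scan before the landmark: 24 for week 26, 48 for week 52.

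- All patients: 2^(−s/m)
- Responders: Σ p·2^(−max(s, f+c)/m) ÷ Σ p·2^(−(f+c)/m)

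Worked for m = 48, c = 12, week 52:

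- All patients: 2^(−48/48) = 0.50.
- Responder denominator: 0.5 × 0.707 + 0.3 × 0.595 + 0.2 × 0.500 = 0.632.
- Responder numerator: 0.500, because max(s, f+c) = 48 for every f.
- Ratio: 0.500/0.632 = 0.79.

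| | m = 36 | m = 48 | m = 72 |
|---|---|---|---|
| Week 26, all | 63% | 71% | 79% |
| Week 26, responders, c = 12 | 100% | 100% | 100% |
| Week 26, responders, c = 4 | 92% | 94% | 96% |
| Week 52, all | 40% | 50% | 63% |
| Week 52, responders, c = 12 | 73% | 79% | 86% |
| Week 52, responders, c = 4 | 62% | 70% | 79% |

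If every first response came at week 12 with c = 4, the 26-week responder figure is 2^(−8/m) = 86%, 89% and 93%.

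**5. If responders really do better.** Suppose patients prone to respond have half the hazard, so their medians are 72, 96 and 144 weeks. Their true 26-week rates are 2^(−24/72), 2^(−24/96) and 2^(−24/144) = 79%, 84% and 89%. Responder-only PFS still gives 100% (c = 12) or 96%, 97% and 98% (c = 4). It exceeds the true rate by 21, 16 and 11 points, or by 17, 13 and 9 points.

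**The case against.** The best counter-argument is that the working analysis text is already right. Section 13.3.4, Section 10.1.1 and the synopsis methods would all lead a statistician to analyse every treated patient, and the 26-, 39- and 52-week PFS rates appear only in Section 13.3.4. An inflated 26-week rate therefore combines a landmark from one section with a population from another. This is fair as a prediction of what would be done, but it does not remove the contradiction, because nothing in the protocol ranks Section 13.3.4 above the endpoint definition.

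The simulated size is also open to challenge. The introduction describes renal tumours kept under surveillance until about 3 cm, so slower progression is plausible. With m = 208 and c = 12 the gap shrinks to 92% against 100% at week 26 and 85% against 95% at week 52. That stands: only the direction of the bias and the patient counts rest on the documents.

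Three smaller points also stand:

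- Section 5.2 is silent on the restriction and does not expressly contradict it.
- Naming the Efficacy Analysis Set in Section 13.3.5 does not prove that non-responders are included, since Section 13.3.4 also summarises DOR and TTR within subgroups of that set.
- The idea of a misplaced clause is an inference. The synopsis has the clause on PFS and TTR but not on DOR, which suggests a slip; Section 10.1 has it on all three.

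Finally, the separate SAP may already settle the population. It was not available to check.

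**Conclusion.** The concern holds. Two endpoint bullets restrict ccRCC PFS to confirmed responders, and the rest of the plan points to all treated patients. Applied as written, the bullets give a wrong result: PFS in about 7.5 to 15 of 50 patients at the design response rates, 74% left out at the success boundary, and a 26-week rate at or near 100% by construction if confirmation is at the next scheduled scan. The percentage gaps in the illustration depend on assumed progression rates and response timing; the contradiction and the counts do not.

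This should be fixed but does not threaten the trial's main conclusion. PFS is a descriptive secondary endpoint, and neither the Stage 2 gate nor the 13/50 ORR decision uses it.

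**What to change.** - In the PFS bullet of the synopsis and of Section 10.1, delete the clause limiting the calculation to patients with a best confirmed CR or PR.
- State in both places, in Section 13.3.4 and in the SAP that ccRCC PFS is analysed in the full Efficacy Analysis Set. The SAP has to carry this wording because Section 13 gives it the last word.
- Keep the responder restriction for DOR and TTR only, and add it to the synopsis DOR bullet so that it matches Section 10.1.

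The cost is one clause deleted in two bullets, one clause added, and one sentence naming the analysis set. Data collection, sample size and the primary decision do not change.
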